#### **1.3.1 Overview**

In the first portion of this study, cohorts of subjects will be treated with increasing doses of trigriluzole in combination with nivolumab. After the MTD of trigriluzole is identified, it will be tested in combination with pembrolizumab. The MTD of trigriluzole with nivolumab is likely to be safe and tolerable with pembrolizumab. The sequential design is justified because nivolumab and pembrolizumab are both PD-1-blocking antibodies and there are no discernible differences in the safety profiles. Thus, the data obtained from the pembrolizumab group are not independent of the data in the nivolumab treatment group. The sequential design limits the size and the cost of the trial.

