Pembrolizumab has been studied at weight-based doses of 2 and 10 mg/kg every 2-3 weeks and a flat dose of 200 mg every 3 weeks. In melanoma patients previously treated with ipilimumab, the response rate was 29%. In the previously untreated population, the response rate was 45% and the 1-year overall survival rate was 73%. In patients with non-small cell lung cancer whose tumor cells have high PD-L1 expression (defined as 50% or more), pembrolizumab treatment was associated with median overall survival that was 7-9 months longer than standard chemotherapy. In October 2016, the FDA approval for pembrolizumab was extended to include first-line treatment of patients whose tumors have high PD-L1 expression.

Overall, across these cancers, the anti-PD-1 agents have response rates of 20-45% , meaning that the majority of cancer patients do not achieve an objective response to single-agent treatment. Patients whose tumors lack immune cell infiltration more often fail to respond to anti-PD-1 and anti-CTLA-4 therapies, which highlights the importance of the

Protocol Number: RCINJ# 051707

PI Name: [name]

Protocol Title: A Phase I Study to Evaluate the Safety of Trigriluzole (FC-4157/BHV-4157) in Combination with PD-1 Blocking Antibodies

18

RESERVED FOR IRB STAMP  
DO NOT MODIFY THIS SPACE

Form Version v120116

IRB ID: Pro20170000453  
Approval Date: 10/4/2019  
Expiration Date: 4/3/2020

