### **Inclusion Criteria**

A patient/subject is eligible for enrollment if *all* of the following inclusion criteria are met.

- 1) Patients must have histologically confirmed solid malignancy or lymphoma that is metastatic or unresectable
- 2) There is reasonable expectation of response to pembrolizumab or nivolumab, and one of the drugs is available from the commercial supply. This includes (but is not limited to) the following tumor types: melanoma, non-small cell lung cancer, renal cell carcinoma, squamous cell carcinoma of the head and neck, bladder cancer, and classic Hodgkin lymphoma.
- 3) The patient must have failed at least one line of standard treatment, with the following exceptions in which a PD-1 antibody is FDA approved in the first-line setting:
  - a. melanoma patients
  - b. non-small cell lung cancer patients without EGFR or ALK genomic tumor aberrations whose tumors have high PD-L1 expression [(Tumor Proportion Score (TPS)  $\geq 50\%$ )] as determined by an FDA-approved test.
- 4) Age  $\geq 18$  years old
- 5) Patients must give informed consent.
- 6) Prior chemotherapy, immunotherapy, radiotherapy or major surgery (including radiation therapy or surgery for treatment of brain metastases) must be

completed at least 3 weeks before study entry. Prior PD-1 or PD-L1 therapy is acceptable.

- 7) Patients must have an ECOG performance status  $\leq 2$  (Appendix A).
- 8) Patients must have normal organ and marrow function as defined below:
  - a. Hemoglobin  $>8.0$  mg/dL (without transfusion in the preceding 7 days)
  - b. Platelets  $\geq 70,000$  / $\mu$ L
  - c. Total bilirubin within normal institutional limits (patients with Gilbert's Syndrome must have a total bilirubin  $< 3.0$  mg/dL).
  - d. AST(SGOT)  $<2X$  institutional ULN
  - e. ALT(SGPT)  $<2X$  institutional ULN
- 9) Patients must have measurable disease, defined as at least one lesion that can be accurately measured in at least one dimension (longest diameter to be recorded) as  $\geq 10$  mm by CT scan, PET/CT scan, MRI or caliper/ruler measurement by clinical exam. Lymph nodes: to be considered pathologically enlarged and measurable, a lymph node must be  $\geq 15$  mm in short axis when assessed by CT scan. Lesions that have been radiated in the advanced setting cannot be included as sites of measurable disease unless clear tumor progression has been documented in these lesions since the end of radiation therapy.
- 10) Ability to swallow pills

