#### **4.1.8 Risks to Subjects**

##### **Physical Risk of Study Treatments**

Adverse events are expected to occur on this study. Please see section on expected toxicities. These risks are acceptable because pembrolizumab and nivolumab are both FDA-approved drugs for this indication so the risks are within what is acceptable for standard of care. Trigriluzole is an investigational drug, but the related drug riluzole is also FDA-approved and toxicities are expected to be mild. The risks of the combined study treatment are minimized by careful assessments by trained study staff, as well as frequent laboratory monitoring for safety. Once treatment arm assignment takes place, subjects will be treated and monitored according to the study calendar. Treatment is dosed IV once every 2-3 weeks only after clinician and laboratory assessment. Trigriluzole is self-administered by subjects at home as oral daily to twice daily dosing—subjects will be given clinic phone numbers and after-hours contact information and be instructed to call for guidance if they develop any side effects in between the in-person assessments. Pembrolizumab or nivolumab treatment is dosed IV once every 2-3 weeks only after clinician and laboratory assessment. Trigriluzole is self-administered by subjects at home as oral dosing. To minimize risk, subjects will be given clinic phone numbers and after-hours contact information and be instructed to call for guidance if they develop any side effects in between the in-person assessments.

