#### **Escalation Procedure**

There 4 dosing cohorts of trigriluzole (Cohorts -1, 1, 2, 3, and 4). Please refer to dosing cohort tables.

Starting with Cohort 1, dose escalation of trigriluzole with nivolumab will proceed up to a maximum of 280 mg PO BID (Cohort 4) to identify the MTD. Subjects will be enrolled on the trial in a starting cohort size of 3 subjects.

After the MTD of trigriluzole with nivolumab is identified, the MTD of trigriluzole will be tested in combination with pembrolizumab in 3-6 patients in Cohort P1. If the MTD is not tolerable in Cohort P1, the dose will be decreased by 1 level.

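### The hemoglobin floor is written in mg/dL and so excludes nobody as worded, and inclusion criteria 2 and 3 are not tied to the antibody that the open cohort gives; for untreated high-PD-L1 lung cancer this conflicts with the protocol's own background and risk statement.

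*Combined protocol and SAP*

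**What the plan says.** **Eligibility (4.1.1, Inclusion Criteria).** Criterion 2 has two parts: "There is reasonable expectation of response to pembrolizumab or nivolumab", and "one of the drugs is available from the commercial supply". Criterion 3 requires failure of at least one standard line, "with the following exceptions in which a PD-1 antibody is FDA approved in the first-line setting". The exceptions are melanoma (3a) and non-small cell lung cancer with a tumor proportion score of at least 50% and no EGFR or ALK aberration (3b). Criterion 8a sets hemoglobin above 8.0 "mg/dL (without transfusion in the preceding 7 days").

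**Which antibody is given.** Section 1.3.1 says of the first portion of the study that "cohorts of subjects will be treated with increasing doses of trigriluzole in combination with nivolumab". Tables 3 and 4 in 1.7.5.1 agree: every cohort from -1 to 4 receives nivolumab, and pembrolizumab appears only in P1 and P -1. The Escalation Procedure in 6.1 gives the order: "After the MTD of trigriluzole with nivolumab is identified, the MTD of trigriluzole will be tested in combination with pembrolizumab in 3-6 patients in Cohort" (that is, P1).

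**Background and risk.** Section 1.4.7 states that "the FDA approval for pembrolizumab was extended to include first-line treatment of patients whose tumors have high PD-L1 expression". The nivolumab lung cancer evidence in the same section comes from previously treated patients. Section 4.1.8, Physical Risk of Study Treatments, says: "These risks are acceptable because pembrolizumab and nivolumab are both FDA-approved drugs for this indication".

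**The concern.** Criteria 2 and 3 are worded as if either antibody could be matched to the patient. The design does not allow that, because the antibody follows from the cohort open at registration. A patient can thus qualify on the strength of a drug that he or she will not be given. Where the protocol's own background supports only one of the two drugs for a setting, the eligibility text, the treatment assignment and the risk justification no longer agree.

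The hemoglobin criterion is a separate matter. It is an operative threshold, and under Subject Screening (4.1.1) the organ-function criteria, with performance status, are what keep out patients too frail to take part. A floor that no patient can fail does not do this as written.

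At stake are the internal consistency of the eligibility rules and of the risk statement made to the ethics board. No error rate or sample size figure is involved.

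**Working it through.** **1. Hemoglobin unit.** Input: more than 8.0 mg/dL (criterion 8a). Conversion: 8.0 mg/dL ÷ 1,000 = 0.008 g/dL.

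The documents give no distribution of patient values, so I assume a wide range of 3 to 14 g/dL:
- 3 g/dL = 3,000 mg/dL; 3,000 ÷ 8 = 375 times the floor.
- 14 g/dL = 14,000 mg/dL; 14,000 ÷ 8 = 1,750 times the floor.

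Every value in the range passes. If the number 8.0 was meant in g/dL, the written floor is too low by a factor of 1,000. No other hemoglobin threshold appears in the document, so nothing elsewhere corrects it.

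**2. Eligibility set against assignment.**

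| Step | What the text requires or gives |
|---|---|
| Criterion 2, response | Expected for either antibody |
| Criterion 2, supply | Either antibody is enough |
| Criterion 3, waiver of prior therapy | Any PD-1 antibody approved first line |
| Antibody in Cohorts -1 to 4 | Nivolumab only |
| Antibody in P1 and P -1 | Pembrolizumab only, after the MTD |

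Nothing in the document lets the antibody be chosen by indication or supply, and nothing adds a check that the assigned antibody is the one that satisfied the criterion. Two consequences follow.
- *Supply.* The supply condition can be met by the drug that the open cohort does not use. This holds for any tumor type and at either stage.
- *Indication, criterion 3b.* An untreated lung cancer patient with a score of at least 50% meets criterion 3 during escalation and is assigned nivolumab. Section 1.4.7 cites the first-line high-PD-L1 approval for pembrolizumab, and its nivolumab lung data are in previously treated patients. For this patient the criteria do not secure the approval on which 4.1.8 relies.

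**3. Does the same hold for melanoma (3a)?** No. Section 1.4.7 cites results in previously untreated melanoma for both antibodies: response 40% with nivolumab and 45% with pembrolizumab, and 1-year survival 73% with each. No mismatch is shown.

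**4. How much of the trial is exposed?** Inputs from the Sample Size Justification (1.5 and 6.1): 9–21 subjects with nivolumab, 3–6 with pembrolizumab, 12–27 in total. The totals reproduce: 9 + 3 = 12 and 21 + 6 = 27. The nivolumab share is 9/12 = 75% with both minima and 21/27 = 78% with both maxima. Over all pairings it runs from 9/(9 + 6) = 60% to 21/(21 + 3) = 87.5%. This is the share of subjects planned for the stage in which the 3b mismatch can arise. It is not the share mismatched, which would need the number of 3b patients enrolled, and the documents give no figure for that.

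**The case against.** The best case for the plan is that the class-level wording is deliberate. Section 1.3.1 treats the two antibodies as sharing a target and having indistinguishable safety profiles, criterion 2 leaves its list of tumor types open, and the trial runs under an IND. Enrollment need not stay within labelled indications, so the loose phrase may be the one in 4.1.8 and not the criteria. This stands in part: it is one legitimate way to reconcile the text. It does not remove the contradiction, because 1.3.1 argues from target and safety, whereas criteria 2 and 3 and section 4.1.8 rest on supply, expected response and approval.

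The background is also a selection of studies and approvals, not an inventory of labels. This stands in full. That 1.4.7 cites no first-line nivolumab lung approval does not show that none existed.

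On hemoglobin, 8.0 with a transfusion qualifier, in a list headed by normal organ and marrow function, is evidently a unit slip that screening staff would probably read as g/dL. The eligibility checklist is not among the documents, so an error there is only possible. This stands as to practical effect. It does not make the written threshold correct.

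Treating physicians select candidates and the registration desk verifies eligibility (1.3.8, Study Enrollment Procedures). This makes an unnoticed mismatch less likely, but the desk verifies against the criteria as written.

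**Conclusion.** Both criteria are wrong as written, with limited demonstrated reach.

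- **Criterion 8a:** the literal floor is 0.008 g/dL and excludes nobody over the assumed range of 3–14 g/dL. The practical effect is probably small.
- **Criteria 2 and 3:** they can be satisfied by an antibody that the patient will not receive. The indication mismatch is shown for criterion 3b only. The supply gap in criterion 2 is general.

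A reader might infer three stronger things, none of which the documents support. First, that most of enrollment is mismatched: 75–78% (60–87.5% over all pairings) is the planned nivolumab share, and the number actually affected cannot be computed and could be zero. Second, that patients would give up an approved option for an unapproved one: that depends on label information outside these documents. Third, that the toxicity or MTD findings would be distorted: section 1.3.1 reports no discernible difference in safety profile, efficacy is only described, and no affected analysis can be named.

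**What to change.** 1. Check the unit in criterion 8a and correct it in the protocol and in any eligibility checklist that copies it. This review proposes no threshold.
2. Reconcile criteria 2 and 3, 3b in particular, with the cohort assignment (1.3.1; 1.7.5.1 with Tables 3 and 4; Escalation Procedure in 6.1), with the evidence and approvals cited in 1.4.7, and with the risk statement in 4.1.8. The sponsor may do this in the criteria, in the background or in the risk statement; which eligibility rule is right is a clinical decision for the sponsor. Whichever is chosen, the text should say whether the conditions on response, supply and first-line approval refer to the antibody of the open cohort or to the class.

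The unit correction costs nothing beyond an amendment line. The reconciliation is a wording amendment and leaves the planned 12–27 subjects unchanged. If the sponsor ties eligibility to the assigned antibody, some untreated lung cancer patients could not enter until the pembrolizumab cohort opens after escalation, a delay of unknown length that should be weighed.

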#### **1.3.3 Screening period/Baseline**

Screening evaluations must be performed no more than 28 days prior to registration. The subject must begin study treatment no more than 14 days after registration. Baseline research blood and tumor samples may be performed anytime prior to the start of therapy. Ideally, the research blood samples should be collected 3-14 days prior to the tumor biopsy, but it is also acceptable to collect them on the same day.

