**RUTGERS | eIRB**  
**APPROVED**

IRB ID: Pro20170000453  
Approval Date: 10/4/2019  
Expiration Date: 4/3/2020

identified by name. This is the point that the patient is considered on study. Patients must not start protocol treatment prior to registration.

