### **1.7.8 Concomitant Medications**

No investigational or commercial agents or therapies other than those described below may be administered with the intent to treat the patient's malignancy.

**Prohibited Medications.** Systemic steroids (other than those used for replacement of adrenal insufficiency) or treatment of irAE are prohibited. If systemic steroids are indicated longer than 8 weeks, the subject must discontinue study treatment. Prophylactic use of Colony stimulating factors (CSFs) is not permitted. They may be used for supportive care and should be discontinued when the event resolves/improves. If needed longer than 4 weeks, the subject must discontinue study treatment.

The following medicines are inhibitors of CYP1A2 and are prohibited (they may increase blood levels of the active form of the drug, riluzole):

- fluvoxamine
- cimetidine
- amiodarone
- efavirenz
- fluoroquinolones (ciprofloxacin, levofloxacin, moxifloxacin, gatifloxacin, ofloxacin or norfloxacin)
- fluvoxamine
- furafylline
- interferon
- methoxsalen
- mibepradil
- ticlopidine

Subjects who are taking one of these medications at screening will be excluded if it cannot be discontinued. Subjects who are prescribed one of these medications (e.g. fluoroquinolone antibiotic for an infection) while on-study should be switched to another antibiotic as soon as the prescription is noted.

**Strongly Discouraged Concomitant Foods and Medications.** Subjects should be strongly discouraged from using potent CYP1A2 inhibitors and inducers that could affect the metabolism of trigriluzole.

The following medicines are CYP1A2 inducers, which may increase the rate of elimination of the active metabolite riluzole, thus decreasing blood levels. The drugs should be discontinued if possible or another medicine may be substituted in its place:

- Insulin
- Omeprazole
- Carbamazepine
- Modafanil
- Rifampin
- Tobacco and nicotine products

Other common medications given for gastroesophageal reflux disease, such as antacids, esomeprazole, pantoprazole, lansoprazole, famotidine, ranitidine are acceptable to take while on study.

Of note, chronic use of nicotine has modest effects on riluzole exposure (i.e., approximately 30 – 35% reduction in exposure). This effect would not compromise subject safety (as it represents a decrease in exposure). Subjects should be encouraged to consider smoking cessation or reduction, which is the standard of care.

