## 1.10 Timetable/Schedule of Events

### Schema

#### Trigriluzole + Nivolumab

#### Trigriluzole + Pembrolizumab

**Trigriluzole + Nivolumab Study Calendar**

	Screening/ Baseline 	Treatment Week									
		Week -2	Week -1	Week 1	Week 3	Week 5	Week 7	Week 9	Q2 weeks (Weeks 11 – 109)	Q4 weeks  (Weeks 13 – 109)	Weeks 13, 25, 37, 49
Scheduling Window (Days):		Within 14 d	±3	±1	±7	±7	±7	±7	±7	±7	±7
Informed Consent	X										
Inclusion/Exclusion Criteria	X										
Demographics and Medical History, including BRAF status	X										
Prior and Concomitant Medication Review	X	X	X	X	X	X	X	X	X	X	X
Assess Baseline Symptoms/Adverse Events and Compliance	X	X	X	X	X	X	X	X	X	X	X
Vital Signs and Weight	X	X	X	X	X	X	X	X	X	X	X
ECOG Performance Status, Physical Examination	X	X		X	X	X	X	X		X	X
Routine Safety Laboratory Studies 	X	X 		X	X	X	X	X		X	X
Serum GGT	X			X			X				X
ECG 		X	X	X			X				X 
Trigriluzole Administration (PO continuous dosing)		X	X	X	X	X	X	X	X	X	X
Nivolumab Administration				X	X	X	X	X	X	X	X
Research Blood Collection for PK 		X		X			X				
Research Blood Collection for correlative science 	X			X			X				X 
Tumor Tissue Collection 	X			X			X				
Tumor Assessment 	X						X				X

Protocol Number: RCINJ# 051707

PI Name: [name]

Protocol Title: A Phase I Study to Evaluate the Safety of Trigriluzole (FC-4157/BHV-4157) in Combination with PD-1 Blocking Antibodies

47

RESERVED FOR IRB STAMP  
DO NOT MODIFY THIS SPACE

Form Version v120116

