### **Analysis Plan for Secondary Endpoints**

Clinical Secondary Endpoints. The frequency of AEs and SAEs will be recorded. Clinical measures of efficacy will be described, including overall survival, progression-free survival, etc. (see Secondary Endpoints above). Descriptive statistical will be used, except where otherwise specified. Continuous variables will be presented by summary statistics (such as mean, median, standard error and 90% CI) and the categorical variables by frequency distributions (i.e., frequency counts, percentages and 90% CI).

Correlatives. We will collect pre- and post-treatment tumor samples from responders and non-responders to test for differences in signal transduction in key pathways (MAPK, Pi3K/AKT), presence of TILs and other immune effector cells, PD-L1 expression, the expression of VEGF, IL-8, CD34, CCL2, M-CSF, and immune-related gene expression profile. We will determine if the presence of GRM1 expression, activating mutations in B-RAF or N-RAS, or PTEN inactivation (or activating B-RAF mutations and PTEN inactivation together) in the pre-treatment tumor samples correlates with response to therapy. We will examine the change in key pathways before and after the trigriluzole monotherapy lead-in period (Baseline vs. Week 1) and compare to the samples taken after exposure to combination therapy (Week 7).

We will also collect pre- and post-treatment peripheral blood samples from responders and non-responders and determine the expression of VEGF, IL-8, CD34, CCL2, and M-CSF, and changes in the quantity and contents of tumor-derived exosomes. We will determine if the expression of these markers in pre-treatment peripheral blood samples correlates with response to therapy. Next, we will compare the pre-treatment and post-treatment blood and tumor samples to see if response to treatment correlates with activation or suppression of signal transduction through the MAPK and PI3K/AKT pathways, changes in immune effector cells in the tumors and peripheral blood, or changes in the quantity or contents of peripheral blood exosomes.

Treatment effect for each patient will be measured as paired differences between pre- and post- measurements of these parameters at various times. Transformation of the data will be performed if appropriate, e.g. log transformation, and hence treatment effect will be expressed on a log scale.

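### The 3-week washout in inclusion criterion 6 does not name targeted or investigational drugs, so an on-drug baseline could confound the Baseline versus Week 1 pathway comparison

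*Combined protocol and SAP*

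**What the plan says.** Inclusion criterion 6 (section 4.1.1) sets the washout. It opens with the therapies covered: "Prior chemotherapy, immunotherapy, radiotherapy or major surgery (including radiation therapy or surgery for treatment of brain metastases) must be". The interval, with a note on earlier checkpoint treatment, comes next: "completed at least 3 weeks before study entry. Prior PD-1 or PD-L1 therapy is acceptable". Four classes are named: chemotherapy, immunotherapy, radiotherapy and major surgery. Targeted, other small-molecule and investigational drugs are not.

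Inclusion criterion 3 makes earlier treatment the usual route in: "The patient must have failed at least one line of standard treatment, with the following exceptions in which a PD-1 antibody is FDA approved" in first line. Those exceptions are melanoma, and PD-L1-high lung cancer without EGFR or ALK aberrations. Criterion 2 also lists renal cell carcinoma among the eligible tumors. Both treatment calendars in section 1.10 collect "Demographics and Medical History, including BRAF status" at screening.

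On registration, section 1.3.8 (Study Enrollment Procedures) says "This is the point that the patient is considered on study". Section 1.3.3 adds "The subject must begin study treatment no more than 14 days after registration", with no minimum delay, and allows baseline research blood and tumor samples at any time before treatment begins.

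Section 1.7.8 restricts treatment during the study: "No investigational or commercial agents or therapies other than those described below may be administered with the intent to treat the patient's malignancy". It does not look back before the first dose.

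Section 6.1 (Analysis Plan for Secondary Endpoints) plans the lead-in comparison: "We will examine the change in key pathways before and after the trigriluzole monotherapy lead-in period (Baseline vs. Week 1"), followed by a comparison with Week 7 samples. The same section identifies the key pathways as MAPK and PI3K/AKT.

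**The concern.** The lead-in is the only period in which trigriluzole is given alone, and the Baseline versus Week 1 comparison is where its own pathway effect would be seen. Identifying markers of response to trigriluzole is a secondary objective (section 1.1.1), and section 1.2 says GRM1 signals mainly through MAPK and PI3K/AKT. If a subject's baseline sample is taken on a drug directed at one of those pathways and the drug is then stopped, the marker can change because of the withdrawal. There is no control group to separate that change from trigriluzole's effect.

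A second, smaller stake is the DLT count. The window opens with the first trigriluzole dose on Day -14 (section 6.1, DLT observation period). Section 1.7.7 names fatigue, nausea, diarrhea and liver injury among the toxicities shared by the two study agents. Late toxicity from a recently stopped drug could resemble these.

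The protocol already uses eligibility to guard both targets. Exclusion 8 removes known HIV-positive patients to protect the correlative work, and exclusion 6 removes active untreated CNS metastases partly because they would confuse adverse event evaluation. Criterion 6 leaves a similar gap for recent targeted therapy.

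**Working it through.** **1. Is there another rule that sets a gap?** The rules that could do so are:

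- Section 1.7.8: bars other anticancer treatment during study therapy, with no look-back.
- Exclusion 9: lists CYP1A2 inhibitors and no kinase inhibitor.
- Exclusion 2: requires recovery only from immune-related events of prior immunotherapy.
- Section 1.3.3: caps the time from registration to treatment at 14 days, with no minimum.

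None sets an interval for an unlisted drug.

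**2. Guaranteed gap from last prior therapy to first trigriluzole dose.** Study entry is taken as registration.

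- Listed classes: minimum 21 days, plus 0 to 14 days from registration to treatment, so a floor of 21 to 35 days.
- Unlisted drugs: no stated minimum before registration, plus 0 to 14 days even if the concomitant ban is taken to start at registration. The floor is 0 days when treatment starts on the day of registration.

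**3. The marker comparison.** Let τ be trigriluzole's mean effect on a pathway marker (log scale if transformed), δ the mean shift caused by stopping a pathway-directed drug, n the number of paired samples and m the number of affected subjects. Then

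expected mean change, Baseline to Week 1 = τ + (m/n)·δ.

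The documents give neither m nor δ. They give 12 to 27 subjects in total. If every subject supplied a pair:

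| m (assumed) | n = 12 | n = 27 |
|---|---|---|
| 0 | 0 | 0 |
| 1 | 1/12 = 0.083 δ | 1/27 = 0.037 δ |
| 3 | 3/12 = 0.25 δ | 3/27 = 0.111 δ |

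Fewer pairs give a larger fraction for the same m. Section 1.8 makes research biopsies optional, while section 4.1.8 calls them mandatory, so the number of tumor pairs is uncertain. The sign of δ is open. Rebound after a suppressed baseline could hide an inhibitory effect of trigriluzole, and a delayed effect of the earlier drug could mimic one.

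**4. The DLT rule.** Inputs from section 6.1: target 0.30, both interval margins 0.05, cohorts of 3. A uniform Beta(1,1) prior is assumed. The mTPI compares posterior probability per unit length below 0.25 (E), from 0.25 to 0.35 (S) and above 0.35 (D), with posterior Beta(1+x, 1+n−x) for x DLTs in n subjects:

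| DLTs / n | E | S | D | Decision |
|---|---|---|---|---|
| 0/3 | 2.734 | 1.379 | 0.275 | Escalate |
| 1/3 | 1.047 | 1.753 | 0.866 | Stay |
| 1/6 | 2.220 | 2.111 | 0.360 | Escalate |
| 2/6 | 0.974 | 2.241 | 0.819 | Stay |

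These match Table 6. One misattributed event changes 0/3 from escalate to stay. If the next three subjects have no DLT, 1/6 returns to escalate.

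Illustration only: take a true DLT rate of 0.10 and an independent added carry-over risk q per affected subject; both values are assumed. With one of three affected, P(0/3) = 0.9² × 0.9(1−q). With all three affected, it is [0.9(1−q)]³. With none affected, it is 0.9³ = 0.729.

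| q (assumed) | One of three affected | All three affected |
|---|---|---|
| 0.05 | 0.693 | 0.625 |
| 0.10 | 0.656 | 0.531 |
| 0.20 | 0.583 | 0.373 |

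**The case against.** The strongest reply is that the affected population is assumed. The documents mention no subject with a prior kinase inhibitor, melanoma needs no prior line, and recording BRAF status does not show that a BRAF-directed drug was given. This stands: m may be zero. Enrollment of such subjects is nevertheless foreseeable. Criterion 3 admits EGFR- or ALK-altered lung cancer only after a failed line, and renal cell carcinoma likewise.

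A site might read chemotherapy as covering every anticancer drug. The text does not say so, and it lists immunotherapy separately. If that was the intent, a few words settle it.

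Section 6.1 calls the correlative analyses descriptive, concedes that the sample may be too small, and presents them as feasibility work for larger trials. This limits the consequence, since no trial decision rests on them. A descriptive change can still be confounded and carried into later work.

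The DLT count has real safeguards. An event must be Grade 3 or higher and judged related to study treatment (section 6.1). A preexisting condition counts as an adverse event only if it worsens (section 1.7.11). Criterion 8 limits bilirubin, AST and ALT at entry. Symptoms are assessed at screening and Week -2. These reduce the carry-over risk, though nothing requires recovery from non-hepatic toxicity of an earlier targeted drug.

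The medication review at screening already gathers prior therapy. That is so, but a last-dose date is not specified.

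**Conclusion.** The omission is real and worth correcting. On the literal text, the guaranteed gap is 21 days for the listed classes and 0 days for targeted, other small-molecule and investigational drugs, and the baseline research sample may be taken on such a drug. The main consequence is possible confounding, in either direction, of the descriptive Baseline versus Week 1 comparison of MAPK and PI3K/AKT. Its size is (m/n)·δ, with m and δ unknown. DLT carry-over is secondary: one misattributed event costs an escalation at 0/3. It may cost no more than three further subjects, although the rule in section 6.1 that stops at six patients on a dose leaves that next step unclear.

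The documents do not support several stronger inferences that a reader might draw:

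- **That the DLT window is contaminated for the whole lead-in.** Dividing the lead-in by the DLT window only compares two lengths. How long a stopped drug's effects last is not in the documents.
- **That VEGF is part of the lead-in comparison.** That sentence covers the key pathways only. VEGF enters through the general pre- and post-treatment comparisons in tumor and blood.
- **That regrowth after withdrawal distorts the Week 7 response.** The documents give no basis for judging this, and timing the research samples would not change the timing of the baseline scan.

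**What to change.** 1. State in criterion 6 that the washout applies to all systemic anticancer therapy, including targeted or small-molecule and investigational agents. The interval is for the sponsor to set, together with the date from which it counts.
2. In section 1.3.3 and the calendar footnotes, require baseline research blood and biopsy to be taken after that interval.
3. Record the last-dose date of prior anticancer therapy on the case report form.
4. In section 6.1, show the Baseline versus Week 1 MAPK and PI3K/AKT changes for all subjects, and again without those whose last therapy was directed at these pathways.

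The cost is a few words in the eligibility and sampling text, one date field and one descriptive display. Some subjects will start later, and the second display may rest on few pairs, so it should be read as a check and not as an estimate.
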